5.2.4 Neuropsychiatric Inventory – Clinician Rating Scale (NPI-C)

The complete NPI-C, which includes agitation and aggression domains, will be administered at Baseline and Weeks 12, 28 and 52/ET visits while only the NPI-C agitation and aggression domains will be administered at Weeks 2, 4, and 8 visits.

The NPI-C is a scale to assess the 14 neuropsychiatric symptoms (domains) in patients with dementia. For each domain, there are three NPI-C sections: caregiver interview, patient interview and clinician rating. The caregiver interview includes the frequency (0-4), severity (0-3) and distress (0-5) scores. The subject interview consists of the subject-reported frequency score (0-4). The clinician rating is a clinical impression severity score (0-3) based on all available interview information. For the caregiver interview, if a response of 0 is selected for the frequency score, then the severity and distress scores will be set to 0. For each domain, the domain score is the sum of the clinical impression severity scores within each domain, with higher scores denoting more serious symptoms. Before deriving any combined domain scores, if there are any missing items, the individual domain score will be imputed as follows:

For the delusions, hallucinations, aggression, elation/euphoria, aberrant motor disturbance, sleep disorders, appetite and eating disorders, and aberrant vocalizations domains, if only 1 item is missing then the respective domain score will be imputed by replacing the missing item with the mean of the non-missing items (rounded to the nearest integer) for that subject and timepoint within the domain. If more than 1 item is missing then the respective domain score will be missing.

For the agitation, dysphoria, anxiety, apathy/indifference, and irritability/lability domains, if up to 2 items are missing then the respective domain score will be imputed by replacing each missing item with the mean of the non-missing items (rounded to the nearest integer) for that subject and timepoint within the domain. If more than 2 items are missing then the respective domain score will be missing.

For the disinhibition domain, if up to 3 items are missing then the respective domain score will be imputed by replacing each missing item with the mean of the non-missing values

(rounded to the nearest integer) for that subject and timepoint within the domain. If more than 3 items are missing then the respective domain score will be missing.

Table 3 NPI-C Domain Score

NPI-C Domain	# items	Domain Score Range	Maximum Missing Items Allowed for Deriving the Domain Score*
Delusions	8	0 – 24	1
Hallucinations	7	0 – 21	1
Agitation	13	0 – 39	2
Aggression	8	0 – 24	1
Dysphoria	13	0 – 39	2
Anxiety	14	0 – 42	2
Elation/Euphoria	6	0 – 18	1
Apathy/Indifference	11	0 – 33	2
Disinhibition	16	0 – 48	3
Irritability/Lability	12	0 – 36	2
Aberrant Motor Disturbance	9	0 – 27	1
Sleep Disorders	8	0 – 24	1
Appetite and Eating Disorders	9	0 – 27	1
Aberrant Vocalizations	8	0 – 24	1

* For each domain, the maximum number of missing items allowed for deriving the domain score is the nearest integer to but $\leq 20\%$ of the total items in that domain. If there are any missing items, the individual domain score will be imputed first before calculating the combined domain scores.

The NPI-C combined agitation and aggression domain score is calculated as the sum of the agitation domain score and the aggression domain score. If either the agitation or aggression domain score is missing, the NPI-C combined agitation and aggression domain score will be missing.

The NPI-C combined delusions and hallucinations domain score is calculated as the sum of the delusions domain score and the hallucinations domain score. If either the delusions or hallucinations domain score is missing, the NPI-C combined delusions and hallucinations domain score will be missing.

The NPI-C combined dysphoria and apathy/indifference domain score is calculated as the sum of the dysphoria domain score and the apathy/indifference domain score. If either the

dysphoria or apathy/indifference domain score is missing, the NPI-C combined dysphoria and apathy/indifference domain score will be missing.

The NPI-C total score is calculated as the sum of all 14 individual domain scores. The NPI-C total score ranges from 0 to 426, with higher scores denoting more serious symptoms. After applying the preceding data handling rules, if any of the domain scores remain missing, the total score will be missing.

5.2.5 Modified Alzheimer’s Disease Cooperative Study – Clinical Global Impression-Change (mADCS-CGIC)

The mADCS-CGIC is assessed at Baseline, Weeks 2, 4, 8, 12, 20, 28, 36, 44, and 52/ET visits.

The mADCS-CGIC scale will be used to allow the Investigator to determine the subject’s overall clinical condition as it relates to their symptoms of agitation and aggression, and to address the clinical significance of changes from Baseline in other psychometric measures. The mADCS-CGIC interview will be performed by the Investigator or a medically qualified rater. After completion of the interview, the rater will be asked to rate the subject’s symptoms of agitation and aggression relative to the Baseline interview from the parent study (ACP-103-032), using a standardized 7-point scale (1 = marked improvement to 7 = marked worsening). Higher scores denote worsening or less improvement in agitation and aggression symptoms.

Missing mADCS-CGIC scores will not be imputed.

5.2.6 Karolinska Sleepiness Scale (KSS)

KSS is assessed at Baseline, Weeks 12, 28 and 52/ET visits.

The KSS is a self-reported subjective measure of a subject's level of drowsiness. With the modified version, respondents must choose which of nine statements (1 = extremely alert to 9 = very sleepy, great effort to keep awake, fighting sleep) most accurately describes their level of sleepiness over a period of time, which for this study will be “on average over the previous week”. Higher scores denote more drowsiness.

Missing KSS scores will not be imputed.

5.2.7 Mini-Mental State Examination (MMSE)

MMSE is assessed at Baseline, Weeks 4, 8, 12, 20, 28, 36, 44, and 52/ET visits.

The MMSE is an 11-area, 30 items questionnaire that is used to measure cognitive impairment, with lower scores indicating more severe cognitive impairment.

The total score (0-30) is calculated as the sum of the 30 item scores. If there are less than or equal to 6 missing items then the total score will be imputed as the mean of the non-missing values multiplied by 30 and rounded to the nearest integer for that subject and timepoint. If there are more than 6 missing items then the total score will be missing.

5.2.8 Global Clinician Assessment of Suicidality (GCAS)

Global Clinician Assessment of Suicidality (GCAS) is assessed at Baseline, Weeks 2, 4, 8, 12, 20, 28, 36, 44, 52/ET and Follow-up (if applicable) visits.

The GCAS will be used to assess the occurrence of treatment-emergent suicidal ideation and behavior. The GCAS is a clinician-rated, 5-point scale (0–4) that is designed to rate the subject’s suicidality based on the report of the subject, the report of the study partner/caregiver, and the clinician’s global assessment. Ratings can be 0 (“Absent”), 1 (“Feels life is not worth living”), 2 (“Wishes he/she were dead or any thoughts of possible death to self”), 3 (“Suicidal ideas or gesture”), or 4 (“Attempt at suicide”). The Investigator will record a subject rating, a partner/caregiver rating, and a clinician rating. For a rating of 3 or 4 based on the clinician’s assessment, the date of event will be recorded. At each visit, suicidality since the previous visit will be assessed.

Missing GCAS scores will not be imputed.

5.3 Analysis Visit Windows

In general, the open-label Baseline assessment will be defined as the last non-missing assessment, including those from repeated and unscheduled measurements, before or on the first open-label dose date. Exceptions to this definition will be handled on a case by case basis.

Efficacy and safety assessments will be summarized by analysis visit as presented in Table 4 below.

Table 4 Analysis Visit Windows

Open-label (OL) Analysis Visit Name	Target Study Day¹	Study Day Interval
OL Baseline	1	≤1(based on the first open-label dose date)
OL Week 2	15	2 to 21
OL Week 4	29	22 to 42
OL Week 8	57	43 to 70
OL Week 12	85	71 to 112

OL Week 20	141	113 to 168
OL Week 28	197	169 to 224
OL Week 36	253	225 to 280
OL Week 44	309	281 to 336
OL Week 52	365	337 to 379
OL Follow-up	395	380 – maximum

¹ If the assessment date \geq first open-label dose date, study day = assessment date – first open-label dose date + 1; otherwise study day = assessment date – first open-label dose date. Study day 1 is the first open-label dose date.

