3 STUDY DESIGN

3.1 Overall Study Design

This study is an open-label extension study of the safety and tolerability of pimavanserin for the treatment of agitation and aggression in subjects with probable AD ([McKhann et al. 2011](#)). This study will be conducted as a 52-week, open-label, flexible-dose extension of Study ACP-103-032. Subjects in Study ACP-103-033 must have completed ACP-103-032 and must meet eligibility criteria.

Study ACP-103-033 subjects **must be** consented prior to the final procedures being performed for Study ACP-103-032 at Week 12. Procedures from the Week 12 visit of Study ACP-103-032 will be carried over to the ACP-103-033 study to be included as baseline information and this visit will be considered the Baseline Visit (Visit 1) of the ACP-103-033 study.

Study periods:

- Open-label treatment period (Baseline through 52 weeks of treatment)
- Safety follow-up period (~30 days after the last dose of study drug)

Treatment Period (Baseline through Week 52)

All subjects will receive once daily (QD) doses of pimavanserin (active study drug) over 52 weeks of treatment, starting with 20 mg a day. At the Week 2 visit, the pimavanserin 20 mg dose may be increased to 34 mg a day based on the Investigator's assessment of clinical response. The Investigator may then adjust the dose from 20 mg to 34 mg or from 34 mg to 20 mg at any visit based on clinical response. A dose change at a time other than at a scheduled clinic visit will require an unscheduled visit to dispense the appropriate dose of study drug. Unscheduled clinic visits may occur as needed.

During the Treatment Period, clinic visits will be conducted at Baseline and Weeks 2, 4, 8, 12, 20, 28, 36, 44, and 52, or upon early termination (ET) from the study.

It is recommended that the study drug be taken at approximately the same time each day.

Doses of concomitant or over-the-counter medications should not exceed those indicated for Permitted and Prohibited Concomitant Therapy and Rescue Medication (see [Section 5.6](#)).

Follow-up of Study Completers

A follow-up safety assessment will be conducted via telephone approximately 30 days after the last dose of study drug for subjects who complete the 52-week treatment period and for those who discontinue prematurely from the study.

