3.4.10 Visit 11 (30-day Safety Follow-up, Week 56, Telephone)

- Assessment of concomitant medications/procedures
- Assessment of AEs
- GCAS

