5.3.1 Unscheduled Assessments

Both scheduled and unscheduled assessments, including early termination visits, will be considered for planned timepoint summaries. All assessments will be presented in data listings.

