5.3.2 Multiple Measurements within Visit Windows

If more than one assessment falls within a given window then the assessment closest to the target study day will be selected for the by-visit summaries. If two assessments are equidistant from the target day then the chronologically last assessment will be used for summary. Exceptions may be made for incomplete assessments, in which case, more complete assessments may be given priority. Details are provided in a separate programming conventions document.

For safety summaries where the most extreme values should be selected, e.g. overall post-Baseline minimum, overall post-Baseline maximum and potentially clinically important values for overall post-Baseline summaries, all non-missing post-Baseline values should be considered, regardless of whether the value is selected for the by-visit summaries. All results will be presented in data listings.

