13 METHODS OF EFFICACY ANALYSES

13.1 Exploratory Efficacy Analyses

Descriptive statistics for all exploratory efficacy endpoints listed in [Section 12.1](#) will be tabulated by double-blind treatment group at each scheduled timepoint. The summaries of the change from Baseline results will be presented in two ways as specified in [Section 5.1](#), by double-blind treatment group at each scheduled timepoint.

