14.6 Other Safety Variables

14.6.1 Suicidal Ideation and Behavior

GCAS is assessed at Baseline, Weeks 2, 4, 8, 12, 20, 28, 36, 44, 52/ET and Follow-up (if applicable) visits.

The number and percentage of subjects for each GCAS rating (0-4) based on clinician's assessment will be tabulated by visit, using the number of subjects with non-missing GCAS score for the given visit and double-blind treatment group as the denominator for the percentages. The number and percentage of subjects reporting any post-Baseline GCAS score of 3 or 4 based on clinician's assessment will also be tabulated, using the number of subjects with at least 1 post-Baseline GCAS score for the given double-blind treatment group as the denominator for the percentages.

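### SAP Table 4 counts OL Follow-up from first dose, so the Visit 11 suicidality rating (GCAS) of a subject who stops before about day 350 is assigned to an OL Week row

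*SAP*

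**What the plan says.** SAP 5.3 applies one set of windows to all assessments: "Efficacy and safety assessments will be summarized by analysis visit as presented in Table 4 below". Study day 1 is the first open-label dose. The OL Week windows run without a gap from day 2 to day 379, and OL Follow-up covers day 380 onward, with target day 395.

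SAP 5.3.1 adds: "Both scheduled and unscheduled assessments, including early termination visits, will be considered for planned timepoint summaries". When several records share a window, SAP 5.3.2 says that "the assessment closest to the target study day will be selected for the by-visit summaries", and a tie goes to the later record.

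Protocol 3.1 times the follow-up telephone contact from the other end of treatment: "approximately 30 days after the last dose of study drug for subjects who complete the 52-week treatment period and for those who discontinue prematurely". Protocol 3.4.10 and SAP 5.2.8 include GCAS at that contact. SAP 5.2.8 also defines the period rated: "At each visit, suicidality since the previous visit will be assessed". SAP 14.6.1 tabulates GCAS by visit, "using the number of subjects with non-missing GCAS score for the given visit and double-blind treatment group as the denominator".

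Nothing in SAP 5.3 to 5.3.2 sets a last-dose cut-off or keeps the nominal Visit 11 record out of the OL Week windows.

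**The concern.** The two clocks agree only for completers and very late stoppers. For anyone else, the follow-up call falls before day 380 and its GCAS rating is labelled as an OL Week visit.

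Take a subject whose last dose and ET visit are on day 100. The ET rating falls in OL Week 12 (days 71 to 112). The call on day 130 falls in OL Week 20 (days 113 to 168). The subject then counts in the Week 20 numerator and denominator with a rating that describes days 100 to 130, after drug was stopped.

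GCAS is a named safety endpoint. Its by-visit table would mix ratings made during treatment with ratings of the period after it under one label. The OL Follow-up row that the SAP itself created would hold almost no early stoppers.

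A related gap concerns ET results. Several measures are scheduled at only some visits, and the SAP does not say where an ET value appears if its study day falls in a week where the measure is not scheduled.

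**Working it through.** **Inputs.** Table 4 gives the windows, as study days: Week 2, 2–21; Week 4, 22–42; Week 8, 43–70; Week 12, 71–112; Week 20, 113–168; Week 28, 169–224; Week 36, 225–280; Week 44, 281–336; Week 52, 337–379; Follow-up, from 380. The call is at last dose + 30 days (protocol 3.1), or + 37 if the +7-day window in protocol Appendix A is used in full. The early-stop range is days 2 to 363 (the end matches the under-52-weeks category in SAP 10.1.1; the range is a choice made for this check).

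**Table 4's own figures.** Target day = 7 × week + 1 reproduces all nine OL Week targets (for example 7 × 20 + 1 = 141). Follow-up is 365 + 30 = 395. The table is therefore built for a subject who completes 52 weeks.

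**Days in range, by window.** 20 + 21 + 28 + 42 + 56 + 56 + 56 + 56 + 27 = 362, where 27 is days 337 to 363.

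**Which stop days reach OL Follow-up.** For last dose on day L and a call g days later, the condition is L + g ≥ 380.
- g = 30: L ≥ 350, so days 350–363 (14 days). In an OL Week window: 362 − 14 = 348 (96%).
- g = 37: L ≥ 343, so days 343–363 (21 days). In an OL Week window: 362 − 21 = 341 (94%).

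**Which rating is tabulated.** Being assigned to a window is not the same as being selected. The closest-to-target rule was applied to each stop day, with scheduled visits on target up to the stop day and no unscheduled GCAS:

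| ET after last dose | Call after last dose | Follow-up GCAS tabulated | Only rating in window | Replaces another rating |
|---|---|---|---|---|
| 0 days | 30 days | 288 | 219 | 69 |
| 0 days | 37 days | 300 | 254 | 46 |
| 7 days | 30 days | 263 | 172 | 91 |
| 7 days | 37 days | 281 | 212 | 69 |

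The range is 263/362 = 73% to 300/362 = 83%. Spreading scheduled visits over the protocol windows by simulation gives 73% to 82%. A less favourable pairing (ET 14 days and call 23 days after last dose) gives 212/362 = 59%.

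An example of replacement: with last dose and ET on day 120, ET is 141 − 120 = 21 days from the Week 20 target. The call on day 150 is 9 days from it, so the follow-up rating is used.

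**ET values in a week where the measure is not scheduled (days of 362, ET on the last dose day).**
- ADCS-ADL, KSS, NPI-C total (scheduled Weeks 12, 28, 52): 20 + 21 + 28 + 56 + 56 + 56 = 237 (65%).
- Physical examination (Weeks 12, 52): 237 + 56 = 293 (81%).
- ECG and laboratory tests (Weeks 4, 12, 28, 52): 20 + 28 + 56 + 56 + 56 = 216 (60%).
- NPI-C agitation and aggression domains (Weeks 2, 4, 8, 12, 28, 52): 56 + 56 + 56 = 168 (46%).
- MMSE (all except Week 2): 20 (6%).
- CMAI, ZBI and mADCS-CGIC (every visit): 0.

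**The case against.** **Nothing restricts the by-visit GCAS table to time on drug.** The Safety Analysis Set is everyone with at least one dose, the denominator is non-missing scores, and SAP 14.1 counts adverse events as treatment-emergent up to 30 days after last dose. This stands as far as it goes: the follow-up rating is legitimate safety data and belongs in the report. It does not justify the label. The SAP defines a separate OL Follow-up row, and the same rating goes there for a completer but to an OL Week row for an early stopper.

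**Unseen documents may handle it.** Table specifications are held separately, and SAP 5.3.2 defers details to a programming conventions document. This cannot be excluded. But that deferral concerns choosing among records within a window. On 172 to 254 stop days the follow-up rating is the only one in its window, so such a rule cannot remove it.

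**The numbers per cell are small.** This stands. Assume 20% to 50% of about 111 subjects stop early, all are reached, and stop days are uniform. Then 111 × 0.20 × 0.73 ≈ 16 to 111 × 0.50 × 0.83 ≈ 46 ratings are affected. Over 8 windows (Weeks 4 to 52) and 3 double-blind groups, that is about 0.7 to 1.9 per cell.

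**A stronger reading of the ET gap.** A reader might infer that ET results for ADCS-ADL, KSS, NPI-C or physical examination are lost or wrongly reported. The documents do not show this. SAP 5.3.1 admits ET visits to the planned-timepoint summaries. SAP 13.1 says only that efficacy endpoints "will be tabulated by double-blind treatment group at each scheduled timepoint". Whether an off-schedule value gets a sparse row or none depends on table shells that are not public. Nor does the physical-examination wording prove an undeclared change: protocol 9.7.6 treats Week 52 and EOS/ET as one visit, while SAP 14.5 summarizes Week 52 but writes 52/ET one sentence earlier, so it may be shorthand.

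**Conclusion.** The GCAS point holds. Followed as written, Table 4 assigns the post-drug Visit 11 rating to an OL Week window for every last dose up to day 349 (call at 30 days) or day 342 (call at 37 days). It is then the tabulated value on 263 to 300 of 362 possible stop days, if scheduled visits are on target and ET is 0 to 7 days after last dose.

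These are shares of calendar days. The documents give no distribution of stop dates, so it would be wrong to read 96% or 83% as a share of subjects. It would also be wrong to infer that the study's suicidality conclusion is compromised. The count of subjects with any post-Baseline rating of 3 or 4, the TEAE tables and the listings do not depend on the window label, and no hypothesis is tested. The impact is minor.

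The treatment of off-schedule ET values is an unstated display rule that needs a sentence, not an established error. For ECG and laboratory tests, the overall post-Baseline summaries already include these values.

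**What to change.** Add to SAP 5.3: *GCAS collected at Visit 11 will be assigned to OL Follow-up by nominal visit, whatever the study day, and will not be eligible for an OL Week window.* Table 4 can otherwise stay as it is. The cost is one sentence and one programming condition, with no new data. The OL Follow-up row will then hold ratings from different study days, all about 30 days after last dose.

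As a secondary clarification, state how by-visit tables report an ET value that falls in a week where the measure is not scheduled: in that week's row, in a separate ET row, or in listings only. If a separate ET row is chosen, say whether its values also stay in the by-week rows. Such a row pools different exposure times, so it should stand beside the by-week rows. Apply the rule to all affected measures: ADCS-ADL, KSS, NPI-C total and domains, ECG, laboratory tests, physical examination and MMSE. Reconcile SAP 14.5 with protocol 9.7.6, or list the difference in SAP section 19. The cost is wording and perhaps one extra row in the tables concerned.

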5.3.1 Unscheduled Assessments

Both scheduled and unscheduled assessments, including early termination visits, will be considered for planned timepoint summaries. All assessments will be presented in data listings.

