3.4.9 Unscheduled Visits

Subjects will have the following procedures completed:

- Vital signs (sitting [at least 3 minutes] blood pressure, pulse, respiratory rate, and temperature)
- Assessment of concomitant medications/procedures
- Assessment of AEs
- GCAS

- CMAI and mADCS-CGIC (if the unscheduled visit is to change dose)
- Dispense study drug (if dose changed)
- Study drug accountability (if dose changed)

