5.4 Dosage Adjustments

Dose adjustments will be allowed for pimavanserin based on clinical response. At the Week 2 visit (Visit 2), the pimavanserin 20 mg starting dose may be increased to 34 mg a day based on the Investigator's assessment of clinical response. The Investigator may adjust the dose from 20 mg to 34 mg or from 34 mg to 20 mg at any visit based on clinical response. A dose change at a time other than at a scheduled clinic visit will require an unscheduled visit to dispense the appropriate dose of study drug.

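### SAP 5.3.2 should give scheduled CMAI and mADCS-CGIC scores priority over scores taken at unscheduled dose-change visits

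*SAP*

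**What the plan says.** SAP 5.3.1 sets eligibility: "Both scheduled and unscheduled assessments, including early termination visits, will be considered for planned timepoint summaries". SAP 5.3.2 sets selection when a window holds several assessments: "the assessment closest to the target study day will be selected for the by-visit summaries". On ties: "If two assessments are equidistant from the target day then the chronologically last assessment will be used for summary". The one exception concerns completeness, not visit type: "Exceptions may be made for incomplete assessments, in which case, more complete assessments may be given priority". The section ends by deferring to a document outside the public set: "Details are provided in a separate programming conventions document".

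Protocol 3.4.9 lists, among the unscheduled-visit procedures, "CMAI and mADCS-CGIC (if the unscheduled visit is to change dose"), and footnote h of the schedule (Protocol Appendix A, SAP Table 1) agrees. Vital signs and GCAS, by contrast, are taken at every unscheduled visit.

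Protocol 5.4 lets the Investigator "adjust the dose from 20 mg to 34 mg or from 34 mg to 20 mg at any visit based on clinical response". It adds: "A dose change at a time other than at a scheduled clinic visit will require an unscheduled visit".

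The selected scores feed the by-visit change tables (SAP 13.1) and the responder tables (SAP 13.1.1).

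**The concern.** For these two scales an off-schedule score exists only because someone judged that the subject's response called for a different dose. The measurement is triggered by the outcome it measures. The selection rule ignores this and lets that score replace the planned one on calendar distance alone.

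The two scores are not clearly interchangeable either. Protocol 6.1 has each scale cover the time since the last scheduled assessment, while Protocol 6.1.1 describes CMAI ratings over the prior 2 or 4 weeks. The period covered by a CMAI taken a few days after a planned visit is therefore unclear.

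At stake is whether the by-visit CMAI means, and the CMAI and mADCS-CGIC response rates, describe subjects at planned times or a mixture of planned and response-triggered times. These tables address the exploratory objective on persistence of effect on agitation and aggression.

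**Working it through.** The plan states no figure for this rule, so there is none to reproduce. The check applies the rule to the plan's own calendar.

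**Inputs**
- Visit windows, counted from the Baseline visit: ±3 days (Visits 2-5), ±7 days (Visits 6-9), +7 days (Visit 10). Source: Protocol Appendix A, footnote a.
- First dose on the day after the Baseline visit (Protocol 3.4.3), so a visit at week w plus k days is study day s = 7w + k.
- Target day t = 7w + 1, with the intervals in SAP Table 4. These reproduce as midpoints between targets. Week 20, for example, runs from (85 + 141)/2 = 113 to (141 + 197)/2 - 1 = 168.
- Rule: an unscheduled score on day u displaces the scheduled one if |u - t| < |s - t|, or if these are equal and u > s.

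**Step 1: visit exactly on time.** Here k = 0, s = 7w and |s - t| = 1. Day 7w + 1 is nearer, and day 7w + 2 is equally near and later, so both win. At Week 20, day 140 loses to day 141 and to day 142.

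**Step 2: other visit days.** A scheduled score d days before target is displaced by a score on any of 2d days. A score d days after target is displaced on 2d - 1 days. It is safe only on the target day. A Week 20 visit 7 days early is day 133, so d = 8 and 16 days win (134-149). A visit 7 days late is day 147, so d = 6 and 11 days win (136-146).

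**Step 3: chance of displacement, given one dose-change visit in the window.** The timing is not in the documents, so two assumptions are shown. In both, the scheduled visit is spread evenly over its allowed days.
- A: the dose-change visit is spread evenly over the remaining days of the analysis window.
- B: as A, but with none within 7 days of the scheduled visit.

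| Visit | Window (days) | Winning days: earliest / on time / latest allowed visit | A | B |
|---|---|---|---|---|
| Week 2 | 20 | 8 / 2 / 3 | 18% | 3% |
| Week 4 | 21 | 8 / 2 / 3 | 17% | 1% |
| Week 8 | 28 | 8 / 2 / 3 | 13% | 1% |
| Week 12 | 42 | 8 / 2 / 3 | 8% | 0.5% |
| Weeks 20-44 | 56 | 16 / 2 / 11 | 13% | 5% |
| Week 52 | 43 | on time is earliest: 2 / 2 / 11 | 11% | 3% |

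Examples for A: at Week 12 the winning days over the seven possible visit days total 8 + 6 + 4 + 2 + 0 + 1 + 3 = 24, and 24/(7 × 41) = 0.084. At Week 20 the total over 15 visit days is 108, and 108/(15 × 55) = 0.131. Example for B at Week 12: only the earliest visit day can lose, to 1 of 27 remaining days, so (1/27)/7 = 0.005.

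Week 2 needs a caution. Dose changes start at that visit (Protocol 5.2 and 5.4), so no dose-change score should precede it, yet A spreads them over days 2-21. Restricting A to days after the visit gives (8/10 + 6/9 + 4/8 + 2/7 + 0 + 0 + 0)/7 = 0.32. The Week 2 figure is therefore fixed by assumption, and the 0.5% to 18% range illustrates rather than bounds.

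**Step 4: effect on the CMAI mean.** Shift = share with such a visit × chance of displacement × score difference. Assuming 10-30% of subjects, 0.13 and 10 points gives 0.10 × 0.13 × 10 = 0.13 to 0.30 × 0.13 × 10 = 0.39 points. Assuming instead that 2-10% of subjects have a score replaced and it differs by 5-15 points gives 0.02 × 5 = 0.1 to 0.10 × 15 = 1.5 points. The top of that range is demanding: at 0.13, 10% replaced needs 0.10/0.13 = 77% of subjects with a dose-change visit in one window. The CMAI total runs from 29 to 203.

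**The case against.** The strongest objection is about timing. Displacement usually needs a dose-change visit within days of a scheduled visit, yet the dose can be changed at the scheduled visit itself. An extra trip one or two days later is the least likely pattern. That stands: it is why assumption B gives 0.5% to 5%, and why the 8% to 18% under A cannot be read as expected rates.

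Second, a reader might infer that the displacing scores come from subjects doing badly and so bias the means towards worse agitation. The documents do not support that. They speak of clinical response and allow changes in both directions, so the sign is not fixed.

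Third, a reader might quote the early-edge case, where displacement under A reaches 20% (8/41, Week 12) to 42% (8/19, Week 2), as typical of any visit at the edge of its window. At the late edge it is 7% (3/41, Week 12) to 20% (11/55, Weeks 20-44), and 26% (11/42) at Week 52.

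Fourth, when the scheduled visit is missed, an unscheduled score in the window is used. Nothing is displaced there; a real measurement fills a gap.

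Finally, nearest-to-target is a prespecified rule applied uniformly, the endpoints are exploratory with no hypothesis testing, all assessments are listed, and the programming conventions document may contain a priority rule. These points limit the consequence. They do not remove the gap, because a rule that decides which efficacy score is analysed belongs in the SAP.

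**Conclusion.** The point holds as a small, inexpensive improvement. On the documents' own text, a CMAI or mADCS-CGIC score triggered by an assessment of clinical response can replace an existing planned score, and the one-day offset between visit timing and target days means that even a perfectly timed visit is exposed.

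The size is not known. Given a dose-change visit in the window, displacement is roughly 0.5% to 18% under the two timing assumptions, with the Week 2 figure least secure. The shift in a CMAI visit mean is probably a fraction of a point. Both rest on assumed visit timing, visit frequency and score difference, none of which the documents give.

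A reader might also infer that the former double-blind arms are affected unequally. That would follow if their dose-change rates differ, but nothing in the documents shows that they do.

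**What to change.** Add to SAP 5.3.2 that, for the CMAI and mADCS-CGIC by-visit and responder summaries, a scheduled or EOS/ET assessment in the analysis window takes priority, and a score from an unscheduled dose-change visit is used only if the window holds no such assessment. Where a window holds more than one scheduled or EOS/ET score, the present nearest-to-target and tie rules can still choose between them. A summary restricted to scheduled visits could be added as a sensitivity table. Leave the rule for safety extremes, which uses all post-Baseline values, unchanged.

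This brings displacement of an existing scheduled score to zero at every visit. Discarding dose-change scores altogether would go too far: it would create missing windows, and in the summary that counts missing as non-response an observed responder would become a non-responder.

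The cost is one sentence, a visit-type flag in programming, and occasionally using a score slightly further from the target day.
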